# 4.2.7.2.2 Quality of life

Quality of life will be analyzed for CP by cirrhosis status (cirrhosis vs transition to cirrhosis/no cirrhosis) and treatment regimen (2DAA w/o RBV, 2DAA + RBV, 3DAA w/o RBV and 3DAA + RBV).

### Assessment of general quality of life - EQ-5D-5L

The EQ-5D-5L is a health state utility instrument that evaluates preference for health status

(utility). The 5 items in the EQ-5D-5L comprise 5 dimensions (mobility, self-care, usual activities, pain/discomfort, and anxiety/depression) each of which are rated on 5 levels of severity (1: indicating no problem, 2: indicating slight problems, 3: indicating moderate problems, 4: indicating severe problems, 5: indicating extreme problems), and a separate VAS.

Patients' responses to the EQ-5D-5L will be combined into a unique health state using a 5-digit code with one digit from each of the 5 dimensions representing the level of severity. These EQ-5D-5L states will be converted into a single preference-weighted health utility index score by applying country-specific weights (if available) or US weights (if not available). (3)

No imputation will be performed for missing items, and in case of missing items no index score will be calculated.

A summary table will show descriptive statistics (n, mean, median, SD, minimum and maximum) of the index score values and for the VAS values for baseline and the post-baseline time points, as well as changes from baseline, by cirrhosis status and treatment regimen. In addition, analysis of covariance (ANCOVA) will be applied to investigate the effect of the different ABBVIE REGIMENS (± RBV) by cirrhosis status on EQ-5D-5L endpoints at the post-baseline time points using the corresponding EQ-5D-5L baseline values as covariates.

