9.7.5 PRO Questionnaires

The EQ-5D-5L is a health state utility instrument that evaluates preference for health status (utility). The EQ-5D-5L comprises 5 dimensions (mobility, self-care, usual activities, pain/discomfort, anxiety/depression) each of which are rated on 5 levels of severity (1: indicating no problem, 2: indicating slight problems, 3: indicating moderate problems, 4: indicating severe problems, 5: indicating extreme problems), and a separate VAS.

Patients' responses to the EQ-5D-5L will be combined into a unique health state using a 5-digit code with one digit from each of the 5 dimensions representing the level of severity. These EQ-5D-5L states will be converted into a single preference-weighted health utility index score by applying country-specific weights (if available) or US weights (if not available).

No imputation will be performed for missing items, and in case of missing items no index score will be calculated.

A summary table will show descriptive statistics (n, mean, median, SD, minimum and maximum) of the index score values and for the VAS values for baseline and the post-baseline time points, as well as changes from baseline both for the index score values and for the VAS values. In addition analysis of covariance (ANCOVA) will be applied to investigate the effect of the different ABBVIE REGIMENS (\pm RBV and duration) on EQ-5D-5L endpoints using the corresponding EQ-5D-5L baseline values as covariates.

Assessments of work productivity and activity impairment as assessed by the WPAI Hep C v2.0 will be evaluated according to the WPAI-SHP scoring manual. The WPAI yields four types of scores, the results of which will be presented as percentage of impairment from 0 to 100. Higher percentages indicate greater impairment:

1. % absenteeism: percentage of work time missed due to hepatitis C
2. % presenteeism: percentage of impairment while working due to hepatitis C
3. % TWP: percentage of overall work impairment due to hepatitis C
4. % TAI: percentage of general (non-work) activity impairment due to hepatitis C

The WPAI Hep C v2.0 consists of 6 questions aimed at the following targets:

- Q1. currently employed (yes, no)
- Q2. hours missed due to hepatitis C in the last seven days
- Q3. hours missed due to other reasons in the last seven days
- Q4. hours actually worked in the last seven days

Confidential Information

No use or disclose outside AbbVie is permitted without prior written authorization from AbbVie

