#### **Core Population [CP]**

The core population is defined as all patients of the target population (TP) (definition see above), who are adequately treated according to the standard of care and within local label recommendations for their specific disease characteristics (cirrhotic status, genotype). The following patients will be excluded from the CP:

- · Patients with unknown fibrosis status
- · Cirrhotic patients with genotype 1a not receiving ribavirin
- Patients with genotype 1 for whom 2DAA instead of 3DAA is prescribed
- Patients with genotype 4 not receiving RBV

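### The SAP's EQ-5D-5L ANCOVA drops the protocol's treatment-duration term without explanation, and in cirrhotic patients the core-population exclusions tie its ± ribavirin contrast to genotype 1 subtype

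*SAP*

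**What the plan says.** Protocol section 9.7.5 plans an ANCOVA of the regimens over ribavirin use and course length: "RBV and duration) on EQ-5D-5L endpoints using the corresponding EQ-5D-5L baseline values as covariates".

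SAP section 4.2.7.2.2 restates it as follows: "analysis of covariance (ANCOVA) will be applied to investigate the effect of the different ABBVIE REGIMENS (± RBV) by cirrhosis status". The rest of that sentence sets the endpoints and the adjustment: "by cirrhosis status on EQ-5D-5L endpoints at the post-baseline time points using the corresponding EQ-5D-5L baseline values as covariates". No other covariate is named. The same section analyses the core population (CP) by cirrhosis status and by "treatment regimen (2DAA w/o RBV, 2DAA + RBV, 3DAA w/o RBV and 3DAA + RBV".

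SAP section 4.2.1 limits the CP to patients treated "within local label recommendations for their specific disease characteristics (cirrhotic status, genotype", and then lists exclusions. Apart from unknown fibrosis status, these are:

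- on cirrhosis and subtype, "Cirrhotic patients with genotype 1a not receiving ribavirin"
- on the number of DAAs, "Patients with genotype 1 for whom 2DAA instead of 3DAA is prescribed"
- on genotype 4, "Patients with genotype 4 not receiving RBV"

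Both 12- and 24-week courses are planned (SAP section 3.1). EQ-5D-5L is collected at baseline, at end of treatment (EoT) and at the SVR12 and SVR24 visits (SAP Table 2).

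**The concern.** There are two separate problems. First, the SAP analysis is not the one in the protocol. EoT falls at week 12 for some patients and week 24 for others, so a comparison at EoT without a duration term pools different lengths of exposure. The SAP does announce other departures, such as the SVR12 upper window (section 4.1.1) and the replaced shift tables (section 4.2.8.4), but it is silent on this one.

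Second, the CP exclusions decide which genotypes can appear in which regimen group, and the model has no term for genotype 1 subtype. If subtypes differ in EQ-5D-5L after baseline adjustment, for whatever reason, that difference would appear as a ribavirin effect among cirrhotic patients. The analysis serves a stated secondary objective on patient-reported outcomes, and the SAP describes it as investigating the effect of the regimens.

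**Working it through.** The documents give no sample size, SD or effect size for this ANCOVA, so there is no figure to reproduce. The check is structural.

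**Step 1. Model terms side by side.**

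| Term | Protocol 9.7.5 | SAP 4.2.7.2.2 |
|---|---|---|
| ± ribavirin (RBV) | yes | yes |
| Duration | yes | no |
| Cirrhosis status | no | yes |
| Baseline EQ-5D-5L | yes | yes |
| Genotype or subtype | no | no, except through 2DAA/3DAA |

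**Step 2. What the listed exclusions leave.** Cross genotype (1a, 1b, 4), cirrhosis (yes, no), DAA number (2, 3), RBV (yes, no) and duration (12, 24 weeks): 3 × 2 × 2 × 2 × 2 = 48 combinations. Those that remain are:

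- Genotype 1a: 2 cirrhotic (3DAA + RBV, two durations) + 4 non-cirrhotic (3DAA ± RBV, two durations) = 6
- Genotype 1b: 4 + 4 = 8
- Genotype 4: 2 cirrhosis levels × 2 DAA levels × 2 durations, all with RBV = 8

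The total is 22. By regimen cell:

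| Cell | Cirrhotic | Non-cirrhotic |
|---|---|---|
| 2DAA without RBV | empty | empty |
| 2DAA + RBV | 4 | 4 |
| 3DAA without RBV | 1b only | 1a, 1b |
| 3DAA + RBV | 1a, 1b, 4 | 1a, 1b, 4 |

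Both durations remain possible in every non-empty cell. The cirrhotic 1b-only entry takes genotype 1a as the SAP analysis groups do, with mixed and unknown genotype 1 subtypes counted as 1a. If the exclusion is read literally, a few patients of mixed or unknown subtype could remain in that cell.

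**Step 3. What follows.** Among cirrhotic 3DAA patients the group without RBV cannot contain genotype 1a, so RBV and subtype are linked by the population definition. Stratifying by cirrhosis does not help, because the link lies inside the stratum. Within 2DAA no ± RBV contrast exists, and 2DAA + RBV cannot be compared with 3DAA free of genotype.

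**Step 4. Illustration of size (all inputs assumed).** With no true RBV effect, the expected contrast among cirrhotic 3DAA patients is

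(1a share of the RBV group × residual subtype shift) + (excess 24-week share of the RBV group × residual duration shift).

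Assume 120 patients, 40% genotype 1a (all on RBV), half of genotype 1b on RBV, half of genotype 1a and no genotype 1b on 24 weeks, a subtype shift of −0.05, a duration shift of −0.03 and a residual SD of 0.10.

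- 1a share of the RBV group: 0.40 / (0.40 + 0.60 × 0.5) = 0.571
- Subtype part: 0.571 × (−0.05) = −0.029
- Duration part: 0.571 × 0.5 × (−0.03) = −0.009
- Sum: −0.037 from unrounded parts

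A simulation of this setting (3,000 data sets) gave:

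| Model and setting | Mean RBV estimate | False-positive rate at nominal 5% |
|---|---|---|
| SAP model | −0.037 | 43% |
| With subtype and duration added | 0.000 | 5.4% |
| SAP model, no duration shift | −0.029 | 29% |
| SAP model, no duration shift, 20% genotype 1a | −0.016 | 13% |

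These figures show the mechanism. They do not estimate what this study would see, and with a zero subtype shift the subtype part vanishes.

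**The case against.** The strongest reply has five parts.

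- **The study is descriptive and exploratory.** Protocol section 9.9 already names confounding as a limitation, and this analysis carries no hypothesis or alpha. That is true and it limits the weight of the point. A general caveat does not explain why a protocol-specified term was dropped, nor does it remove a link that the CP definition creates.
- **Cirrhosis status partly stands in for duration.** The protocol background describes 12-week therapy in non-cirrhotic trials and 12 or 24 weeks in the cirrhosis trial. This stands: the remaining duration concern lies mainly in cirrhotic patients. The interim analysis is restricted to a planned 12 weeks, so the duration point does not apply there.
- **Genotype is not in the protocol ANCOVA either.** Correct. Only the loss of duration is a departure. Adding subtype is an improvement.
- **Genotype is not wholly ignored.** With four regimen levels, 2DAA versus 3DAA largely separates genotype 4 from genotype 1. What is left unaddressed is 1a versus 1b.
- **A fuller model may strain small cirrhotic cells, and a genotype term is nearly aliased with 2DAA + RBV.** This is fair, and it is why the subtype term belongs among 3DAA patients only.

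A reader might also infer that the CP rules confound ribavirin with course length. They do not: no listed exclusion mentions duration, and both durations are allowed on both sides. Any such link would come from label and prescribing. The same holds for subtype in non-cirrhotic patients, where 1a may appear with or without ribavirin.

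**Conclusion.** The point holds in two limited parts. First, the SAP drops duration from the EQ-5D-5L ANCOVA without a reason; this needs no assumption. Second, among cirrhotic CP patients on three DAAs, the exclusions make the ribavirin-free group genotype 1b only, so the ± ribavirin contrast is mixed with subtype by rule. This rests on the listed exclusions and on the SAP's own grouping of mixed and unknown subtypes with 1a.

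It would be tempting to say that the whole contrast compares patient groups and not regimens, or to attach a fixed bias to it. The documents support neither. Genotype 1b may occur on both sides, the rule-based link is confined to cirrhotic patients, and no EQ-5D-5L inputs are given from which a size could be derived. This is a low-cost improvement to a secondary analysis. The primary SVR12 result is not touched.

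**What to change.** Amend SAP section 4.2.7.2.2 for the final analysis:

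1. Restore planned duration (12 or 24 weeks) as a term, as the protocol specifies. If it is left out, record that as a departure with a reason.
2. Among 3DAA patients, add genotype 1 subtype (1a versus 1b) as a covariate. Alternatively, present the ± ribavirin contrast within genotype 1b on 3DAA, where the CP rules allow both options.
3. State that 2DAA without ribavirin is empty in the CP, and that 2DAA + ribavirin contains only genotype 4 and so cannot be compared with 3DAA free of genotype.
4. Describe the contrasts as descriptive associations, not as effects of ribavirin.

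Age, sex and prior-treatment status are optional.

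The cost is a few SAP sentences. Genotype, subtype and regimen are already collected. The price is a few degrees of freedom, which may matter in small cirrhotic cells, and a less general contrast if it is restricted to genotype 1b.

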#### Assessment of work productivity and activity impairment – WPAI Hep C V2.0

The WPAI questionnaire will be used to measure work absenteeism, work presenteeism, and daily activity impairment. The WPAI Hep C V2.0 is the HCV specific questionnaire that will be used in this study. Respondents are asked about time missed from work and time while at work during which productivity was impaired in the past seven days. Results of WPAI are expressed as a percentage of impairment from 0 to 100, with higher percentages indicating greater impairment and less productivity:

- % Presenteeism percentage of impairment while working due to health problem
- % Absenteeism percentage of work time missed due to health problem
- % Total work productivity impairment (TWP) percentage of overall work impairment due to health problem
- % Total activity impairment (TAI) percentage of general (non-work) activity impairment due to health problem

The WPAI Hep C v2.0 consists of 6 questions aimed at the following targets:

- Q1.currently employed (yes, no)
- Q2.hours missed due to hepatitis C in the last seven days
- Q3.hours missed due to other reasons in the last seven days
- Q4.hours actually worked in the last seven days
- Q5.degree hepatitis C affected productivity while working
- Q6.degree hepatitis C affected regular activities

The four scores will be derived according to the WPAI-SHP scoring manual (4). as follows:

- 1. % absenteeism: 100\*Q2/(Q2+Q4)
- 2. % presenteeism: 100\*Q5/10
- 3. % TWP: 100\*{Q2/(Q2+Q4) + [Q4/(Q2+Q4)]\* Q5/10}

4. % TAI: 100\*Q6/10

The coding rules for contradictory or missing information are:

- If Q1 = YES or Q1 = NO or missing and hours missed or worked > 0, then employed. If Q1 = missing and hours missed and worked = 0, then not employed.
- If hours worked = 0, then productivity while at work is not applicable.
- A score will be set to missing if one or more of the items Q1-6 that are needed for the calculation of the score are missing. No imputation will be performed for missing items.
- Someone who missed all work hours due to health is 100% impaired.

The summary table will present the absolute and relative frequencies of employed and unemployed patients and descriptive statistics (n, mean, median, SD, minimum and maximum) for the four scores for baseline and the post-baseline time points by cirrhosis status and treatment regimen.

Table 9 Overview of Outputs for Secondary Variables

Output Title	Output Short Name	Analysis Population
EQ-5D-5L by Treatment Regimen and Cirrhosis Status - CP - <country></country>	teq _<c>_tc_cp</c>	Core population
WPAI by Treatment Regimen and Cirrhosis Status - CP - <country></country>	twp_ <c>_tc_cp</c>	Core population

The layouts of the tables mentioned above are provided in Part II of the SAP (Table Shells).

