8.2.2 Secondary Objectives

2. To provide real world evidence for predictive factors of virological response
3. To describe the pattern of real world use of the ABBVIE REGIMEN ± RBV with respect to different patient and treatment characteristics
4. To evaluate the influence of adherence on treatment outcome in routine clinical practice
5. To collect information on co-morbidities and concomitant medication in the Polish population
6. To describe the tolerability of the ABBVIE REGIMEN ± RBV

Confidential Information

7. To document the effect of the ABBVIE REGIMEN ± RBV on PROs and work productivity in the Polish population

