Q5.degree hepatitis C affected productivity while working
Q6.degree hepatitis C affected regular activities

The four scores will be derived as follows:

1. % absenteeism: $100 * Q2 / (Q2 + Q4)$
2. % presenteeism: $100 * Q5 / 10$
3. % TWP: $100 * \{Q2 / (Q2 + Q4) + [Q4 / (Q2 + Q4)] * Q5 / 10\}$
4. % TAI: $100 * Q6 / 10$

A score will be set to missing if one or more of the items Q1-Q6 that are needed for the calculation of the score are missing. No imputation will be performed for missing items.

The summary table will present the absolute and relative frequencies of employed and unemployed patients and descriptive statistics for the four scores. Further details of the analysis will be specified in the SAP.

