#### Secondary objectives:

- 2. To provide real world evidence for predictive factors of virological response
- 3. To describe the pattern of real world use of the ABBVIE REGIMEN ± RBV with respect to different patient and treatment characteristics
- 4. To evaluate the influence of adherence on treatment outcome in routine clinical practice
- 5. To collect information on co-morbidities and concomitant medication in the Polish population
- 6. To describe the tolerability of the ABBVIE REGIMEN ± RBV
- 7. To document the effect of the ABBVIE REGIMEN  $\pm$  RBV on PROs and work productivity in the Polish population

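### The WPAI scores are summarised visit by visit with no change from baseline, so differences between visit means mix within-patient change with changes in who contributes a score.

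*SAP*

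**What the plan says.** Secondary objective 7, in both documents, reads: "To document the effect of the ABBVIE REGIMEN ± RBV on PROs and work productivity in the Polish population" (Protocol 8.2.2).

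For WPAI, the SAP's paragraph on work productivity and activity impairment states: "The summary table will present the absolute and relative frequencies of employed and unemployed patients". The same sentence adds n, mean, median, SD, minimum and maximum "for the four scores for baseline and the post-baseline time points by cirrhosis status and treatment regimen". The output is a single table on the core population, `twp_<c>_tc_cp`. Protocol 9.7.5 plans the same employment frequencies and "descriptive statistics for the four scores. Further details of the analysis will be specified in the SAP". Neither document mentions change from baseline, a paired summary or an employment cross-table for WPAI.

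For EQ-5D-5L, the SAP plans descriptive statistics "as well as changes from baseline, by cirrhosis status and treatment regimen", and an ANCOVA with the baseline value as covariate. Protocol 9.7.5 also plans summaries "as well as changes from baseline both for the index score values and for the VAS values", and an ANCOVA.

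**The concern.** A table of visit means invites the reader to subtract the baseline mean from the later one and take the result as the answer to objective 7. That subtraction is safe only if the same patients contribute at both visits. For WPAI there are specific reasons why they may not:

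- Patients not in paid employment skip to question 6 (Protocol Annex 2), so three of the four scores exist only for patients employed at that visit.
- Presenteeism is narrower still. The SAP's coding rule is "If hours worked = 0, then productivity while at work is not applicable".
- A score with a missing required item is set to missing without imputation, and the data schedule collects only what is available from routine practice.

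At stake is whether the work-productivity half of objective 7 can be read from the planned output. The plan already summarises change from baseline for EQ-5D-5L and for laboratory values (SAP 4.2.8.4), and gives no reason for treating WPAI differently.

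**Working it through.** **The plan's own figures.** The documents contain no WPAI figure to reproduce. The only precision figures are the confidence interval widths for SVR12, which do not bear on this point.

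**Which scores are exposed, and to what.**

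| Score | Formula in the SAP | Exists for | Exposed to |
|---|---|---|---|
| Absenteeism | 100·Q2/(Q2+Q4) | employed patients | employment shifts, non-response |
| Presenteeism | 100·Q5/10 | employed patients with hours worked above 0 | employment shifts, weeks with no work, non-response |
| TWP | 100·{Q2/(Q2+Q4) + [Q4/(Q2+Q4)]·Q5/10} | employed patients | employment shifts, non-response |
| TAI | 100·Q6/10 | all patients | non-response only |

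An employed patient who misses the whole week because of hepatitis C leaves the presenteeism mean. The same patient has absenteeism of 100·Q2/(Q2+0) = 100, and the SAP's rule for patients who miss all hours through ill health keeps them at 100% impaired. One event can therefore act differently on different scores.

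**Illustration with no within-patient change.** All inputs are assumed except the 360, which is the lower end of the 360–380 evaluable patients in Protocol 9.5.

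- Assume 50% are employed: 360 × 0.5 = 180 with a work score at baseline.
- Assume each patient has a stable impairment of 10% or 50%, with 20% of the employed in the higher group: 144 at 10% and 36 at 50%.
- Baseline mean = (144×10 + 36×50)/180 = 3240/180 = 18.0.
- Let a fraction d of the higher group stop contributing, through leaving work or not responding. Later mean = (144×10 + 36(1−d)×50)/(144 + 36(1−d)).

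| d | n later | Later mean | Apparent change | Paired change |
|---|---|---|---|---|
| 25% | 171 | 2790/171 = 16.3 | −1.7 | 0 |
| 50% | 162 | 2340/162 = 14.4 | −3.6 | 0 |
| 75% | 153 | 1890/153 = 12.4 | −5.6 | 0 |
| 100% | 144 | 1440/144 = 10.0 | −8.0 | 0 |

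Over the same values of d, the apparent change runs from −0.9 to −4.0 with 10% in the higher group (baseline mean 14.0), and from −2.3 to −12.0 with 30% (baseline mean 22.0).

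**Direction.** The artefact can also run the other way. If half of the lower group stop contributing and all of the higher group remain, the later mean is (72×10 + 36×50)/108 = 2520/108 = 23.3, an apparent worsening of 5.3 points, again with no patient changing.

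**What the planned table would show.** In the row d = 50%, it would show n falling from 180 to 162 and the mean from 18.0 to 14.4. The loss of 18 scores is visible. Whether the 3.6 points come from those 18 patients or from improvement in the other 162 cannot be read from it.

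**The case against.** The strongest reply is that the table already carries a safeguard: employment frequencies and n stand beside the means, so a net shift in employment or response is on view. This stands, and it limits the point. A reader might infer that such shifts would pass unnoticed as a treatment effect, and the documents do not support that. What remains is that marginal counts do not show who moved, and that people leaving and entering work can cancel in them.

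Several other replies also stand:

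- The objective is to document, the analysis is descriptive, there is no untreated comparator, and Protocol 9.9 already acknowledges the difficulty of interpreting treatment effects when data are missing. A reader might infer that paired change would supply a causal effect; it would not.
- A reader might argue from precision, since a paired difference can have a smaller standard error than a difference of independent means. The plan makes no test or interval comparing visits as independent samples, so the argument has no target. The smaller paired n would also offset some of the gain.
- A reader might suspect that the SAP departs from the protocol. It does not: the protocol also plans only descriptive WPAI statistics and leaves the detail to the SAP.
- The table layouts are in Part II of the SAP, which was not available. Change columns may exist there, although the SAP text names them for EQ-5D-5L and not for WPAI.
- Paired change alone can mislead. In the illustration it is zero although impaired patients have left work. This is why employment transitions need to be shown with it.

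**Conclusion.** The point holds as a low-cost improvement. As written, the WPAI summary cannot separate within-patient change from a change in contributors. For absenteeism, presenteeism and TWP the contributors may change through employment as well as non-response; for TAI through non-response only.

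Neither the direction nor the size of any bias can be determined from the documents. The 0.9 to 12.0 point falls and the 5.3 point rise show the mechanism on assumed values and do not predict this study's result. A reader might infer that the planned table will overstate the benefit of the regimen; nothing in the documents establishes that. The conclusion rests on the SAP text and would lapse if the Part II shells already contain change from baseline and employment transitions. SVR12 and the other effectiveness analyses are not affected.

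**What to change.** In `twp_<c>_tc_cp`, for each post-baseline time point (EoT, 12 and 24 weeks after EoT):

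1. Add change from baseline for all four scores in patients with both values: paired n, mean, SD, median, minimum and maximum. A 95% confidence interval is optional; the SAP does not specify one for the EQ-5D-5L changes.
2. Add a cross-table of employment status at baseline against status at that visit, so that patients leaving or entering work are seen beside the paired change.

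Keep the planned visit summaries, and add one sentence to the SAP's WPAI paragraph so that text and shells agree.

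The cost is extra rows, from data already collected. The downside is a smaller n for the paired work scores. The table is split by two cirrhosis categories and four regimens, so the assumed 180 employed patients would average 180/8 = 22.5 per cell before any loss, and some cells will be smaller. The paired results describe only patients with a score at both times and, without a comparator, are not a causal effect; a footnote should say so.
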